4.4 Unscheduled Visits

The investigators will schedule visits based on participant's availability. Every effort will be made to accommodate the participants' scheduling needs. Participants will be given the contact information of [name] for the drug portion of the study. They will be given instructions on how to contact [name] should any issues arise.

4.5 Concomitant Medication

Any concomitant medication deemed necessary for the welfare of the subject during the study may be given at the discretion of the medical monitor and/or Investigator. No more than 2 psychoactive medications (including antiepileptics) may be used with the exception of medications being combined to treat ADHD symptoms and sleep problems. Psychoactive medications must be FDA-approved for use for the disease or symptom being treated; off-label use is not permitted. If the subject is taking fewer than 2 psychoactive medications, and during the study it is deemed the subject needs an additional psychoactive medication, the Medical Monitor must be consulted before the subject can continue in the study. **Antipsychotic medications are not permitted.**

Medications with anxiolytic properties (serotonin re-uptake inhibitors, tricyclic anti-depressants, venlafaxine, buspirone, and propranolol) are not permitted. Additionally, regular use of

benzodiazepines is not permitted. Melatonin, diphenhydramine, and other medications administered regularly for insomnia are permitted.

The use of vigabatrin, tiagabine, riluzole, or racemic baclofen is prohibited.

Examples of psychoactive medications that are allowed for FDA-approved indications are provided in Appendix A. All concomitant medication information, including indication, dose, route and dates of use, must be documented in full in the source notes and case report form (CRF), and should include any changes that have occurred during the study along with the reason for the medication or dose change. Any changes in the doses of concomitant medications should be reported to the Medical Monitor.

4.6 Rescue Medication Administration

There are no antidotes for STX209.

4.7 Subject Completion/Withdrawal

Criteria for withdrawal of subjects and plans for provision of care after withdrawal. Subjects may withdraw from the study at any time without prejudice to their care. They may also be discontinued from the study at the discretion of the Investigator for lack of adherence to study treatment or visit schedules. The Investigator may also withdraw subjects who violate the study plan, or to protect the subject for reasons of safety or for administrative reasons. It will be documented in the CRF whether or not each subject completes the clinical study. If the Investigator becomes aware of any serious, related adverse events after the subject completes or withdraws from the study, they will be recorded in the source documents.

At study completion (Visit 3) a final physical examination will be performed, AE assessed, and subjects debriefed.

4.7.1 Early Termination Study Visit

When a subject withdraws from the study, the reason(s) for withdrawal shall be recorded by the Investigator. Given that this is a study examining the acute effects of STX209 on brain activity, if a subject withdraws, they will be contacted by the study coordinator to elicit AE information.

5 STUDY EVALUATIONS AND MEASUREMENTS

5.1.1 Screening and Monitoring Evaluations and Measurements

Upon entry into this study, we will obtain informed consent/assent, review inclusion /exclusion criteria, clinical symptom ratings and intelligence testing will additionally be performed.

5.1.2 Clinical and Neuropsychological Assessment

Intelligence testing will additionally be performed to ensure no mental retardation. The following instruments will be used:

- 1) ADOS-2 (Autism Diagnostic Observation Schedule- 2nd edition) - (*ADOS-G*; Lord et al. [14]; Lord et al. [15]). *The ADOS-G is a semi-structured standardized assessment using developmentally appropriate social and toy-based interactions in a 30-45 minute evaluation session. The ADOS-G consists of four different modules, each directed at a particular level of language ability. The ADOS-G has been carefully psychometrically validated across a wide*

range of ages and severity levels in autism, and it is widely considered the single best gold standard diagnostic instrument (Lord et al. [16]).

- 2) ADI-R (Autism Diagnostic Interview-Revised) [parent interview] - *(ADI-R; Lord, Rutter, & LeCouteur [16]). The ADI-R will not be administered to control participants or to parents of children with ASD who have already completed an ADI-R with the Center for Autism Research. This interview typically takes 1- 2 hours and primary caregivers will be given the opportunity to complete this measure during the child testing. The ADI-R is appropriate for children 3 and older, and is a structured, standardized parent interview developed to assess the presence and severity of symptoms of autism in early childhood across all three main symptom areas involved in autism: social relatedness, communication, and repetitive and/or restrictive behaviors. The ADI-R has been carefully psychometrically validated across a wide range of ages and severity levels in autism. Considered a gold standard in assessment in autism, this instrument yields an algorithm score and cutoffs for a diagnosis of autism. An algorithm has been established that differentiates autism from other developmental disorders at high levels of sensitivity and specificity (over .90 for both) for subjects with mental ages of 18 months and older.*
- 3) CBCL (Child Behavior Checklist) [parent report] - *This is a parent completed rating scale that asks about behaviors like attention problems, aggression, anxiety, and depression.*
- 4) CELF –IV (Clinical Evaluation of Language Fundamentals- 4th edition) - *This tool evaluates a child's language understanding and expression. This updated version is attached to the eIRB application section 12.02 (2.0).*
- 5) Intervention History Form - *This form is based on one created for the NIH funded autism research network (CPEA: Collaborative Programs of Excellence for Autism). Our revised version is attached in the eIRB application section 12.02 (2.0). It was created by an expert panel of autism treatment researchers from throughout the country, so as to capture information about past treatments. This information can be an important moderating influence on the developmental trajectory of each child.*
- 6) SCQ (Social Communication Questionnaire-Lifetime version) [parent completed measure] - *This is a parent completed rating scale that asks about a child's social and communication skills both over the span of the child's lifetime.*
- 7) SRS-II (Social Responsive Scale, 2nd edition) [parent completed measure] - *This is a parent completed rating scale that asks about a child's social development*
- 8) Vineland Adaptive Behavior Scales (2nd edition) [Parent/Caregiver Rating Form] - *This is a parent completed measure used to support the diagnoses of intellectual and developmental disabilities.*
- 9) WASI-II (Wechsler Abbreviated Scale of Intelligence – 2nd Edition) - *This is a standardized tool that measures a child's problem-solving and reasoning skills.*

Tests will not be administered if results from recent testing (less than 12 months prior to screening visit) are available. Data from tests will only be used if subjects who previously participated in one of our research studies, agreed to share their data on future studies. The ADI-R will be administered only when further classification of subjects is needed

All tests will be promptly reviewed by one of the psychologists on the study team. Any significant clinical concerns on the Child Behavior Checklist or other measures will be verbally reported to the parent-- either in person during the study visit or later via telephone, depending on when the concern

is identified. When indicated, parents will be provided with mental health services referrals or will be advised to take their child to a hospital emergency room in the event of an acute care concern.

5.1.3 Physical Examination

[name] will perform the physical examination (screening visit and visit 3) at the Clinical and Translational Research Center located at [name] or at Main Hospital. However, for the imaging visits (visit 1-visit 3) the SMURF will be performed at the Department of Radiology to assess for adverse events. This can be performed by either [name] or a trained research staff under the guidance and supervision of [name].

- 1) *Physical Examination: A Physical examination will be performed at Screening and at Visit 4. Physical examination findings will be classified using the standard categories listed on the CRF. A brief physical examination will be performed at screening visit and visits 1 through 3 and will include abdominal palpation to assess for liver enlargement, assessing for decreased tone and postural problems, increased drooling and poor orofacial tone, problems holding head up, and difficulty with coordination of motor actions. Any physical examination finding that is judged by the Investigator as a clinically significant change (worsening) from screening visit will be considered an AE, assessed and recorded on the CRF.*
- 2) *Height and Weight: Height and weight measurements must be performed without shoes on, and with only a single layer of light clothing. Height and weight measurements should be performed using consistent units (US).*
- 3) *Medical/Surgical History Review: The study doctor will review Medical/Surgical History*
- 4) *Safety Monitoring Uniform Report Form (SMURF): The SMURF contains a general inquiry, several questions about daily activities (e.g., sleep, appetite, energy level, bowel and bladder function). The general inquiry includes an open ended question about any problems or complaints, as well as questions regarding the need for other medications and doctor or health care encounters since the last study visit. The next section includes 20 to 25 specific queries. These items are rated as not present, mild, moderate or severe. The ratings mild, moderate, or severe are defined as follows: mild=present, but no intervention required; moderate=present, may be bothersome or may require intervention; severe=present, bothersome and requires intervention. The last section includes specific questions about daily activities. All new adverse events (mild, moderate, or severe) will be documented. The status of previously reported adverse events will be monitored as well.*

5.1.4 Vital signs

Depending on availability, vital signs will be measured either by the Imaging techs or [name] at the Department of Radiology. Standard procedures will be followed.

- 1) *Temperature: Temperature will be measured orally using a digital thermometer.*
- 2) *Blood Pressure: Blood pressure will be measured using a Dyna-Map machine. A manual sphygmomanometer will be available for use as needed.*
- 3) *Heart Rate: Heart rate is measured using a Dyna-Map machine.*
- 4) *Respiratory Rate: Respiratory rate will be measured manually.*

5.1.5 Laboratory Evaluations

- *Blood Draw: blood draw testing will include the following: BUN and Creatinine*

*To minimize harm to the subject, in cases where subject is unable to do a blood draw on the day of the screening visit due to anxiety/fear/discomfort if no medical risk factors are identified during medical history review, we will either accept BUN and Creatinine results from an outside source within 3 months of first imaging visit or attempt to do the blood draw on the day of the imaging visit.)

5.1.6 MEG, MRI and MRS Assessment

- 1) **MEG:** During the MEG examination the child will sit or lie on a padded chair / bed with their head positioned inside a scanning helmet. The chair / bed and helmet are housed inside a special room (magnetically shielded room), free from external electromagnetic interference. Inside the helmet are highly sensitive magnetic field detectors which can passively detect brain activity within the head. There is no radiation involved. The helmet may gently touch the child's head, but there is no need for placement of electrodes directly on the scalp. The standard acquisition procedure employed in our studies is to place three fiducial markers (at left and right pre-auricular points and nasion) and instruct subjects to sit very still with their head inside the MEG helmet. In addition to MEG, electrodes at the outer canthi and supra- and suborbitally may be used to monitor EOG. Likewise, an electrode each may be attached to both the right and the left collar bone in order to monitor heartbeat. After attachment of the three localizing head coils and the EOG and cardiac electrodes, the location of points across the surface of the subjects head will be digitized using a Polhemus digitizer for later topographic and source-localization analyses and to facilitate co-registration with structural MRI. The child will be able to see clearly as the helmet covers only the upper and back portions of the head. Earphones will be placed in the child's ears to deliver auditory stimuli at a comfortable listening level (40dB above sensation level). A screen will be placed approximately 12 inches in front of the child's face and will display video images. A variety of auditory stimuli will be delivered. When auditory stimuli are being delivered, the child may watch a DVD movie or cartoons on the video screen. The experimental session is broken down into a series of short (5-10minute) data acquisition periods (see below).

After each task, the child will be able, if they wish, to take a break from scanning. During the entire scanning session, the child will be monitored via closed-circuit video and communication will be possible through an intercom system.

Three MEG recordings will be obtained (at baseline and 60 minutes following acute drug/placebo administration), with each MEG recording session lasting ~30 minutes, and consisting of the following paradigms:

- 1) Resting MEG/EEG: 2 minutes eyes open and 5 minutes eyes closed (7 minutes)
 - 2) Binaurally presented 300 and 500Hz 300ms duration sinusoidal tone (45dB SL), using the task reported in Roberts et al. (2010). (2 minutes)
 - 3) Auditory 40 Hz steady-state task, presenting 200 trials of 40 Hz amplitude modulated (AM) sinusoidal tones (500 ms long, 45 dB SL) with a jittered 1.5 sec inter-stimulus interval. (7 minutes)
 - 4) Oddball auditory task with interleaved /a/ and /u/ vowel stimuli as in Roberts et al. (2011). (12 minutes)
- 2) **MRI/MRS** Magnetic resonance imaging will then be performed using a 3T Siemens Trio MR scanner in the Department of Radiology at Children's Hospital of Philadelphia. This state of the art equipment is equipped with multi-channel RF capabilities (allowing parallel imaging

(Pruessmann et al. [17]). A mock scanner (Nordic Neurolabs) is available for subject conditioning and paradigm practicing. Sequences will include:

- 1) localizer scouts (3-plane)
- 2) inversion-recovery prepped 3D gradient recalled echo imaging sequences for anatomic visualization (high resolution 256x256x160 matrix, isotropic 1mm resolution)
- 3) MEGAPRESS single voxel edited magnetic resonance spectroscopy sequence and analysis, as provided by Siemens Medical Solutions

All of the above MRI sequences are FDA-approved with the exception of the MEGAPRESS. The MEGAPRESS sequence was recently developed and measures brain chemistry (for example GABA). The MEGAPRESS sequence will take approximately 20 minutes and will be obtained for all participants.

The MEGAPRESS MR pulse sequence is not specifically approved by the FDA. It was obtained from Siemens Medical Solutions as a Works-in-progress (WIP #529). The conditions of use of this WIP is that it is not to be used for clinical interpretation and that it should be used under IRB-approved protocols. Technically, it is a very simple modification of the conventional approved MR spectroscopy pulse sequence, in which a mathematical subtraction allows resolution of the previously obscured GABA resonance (by cancelling the overlapping Creatine resonance). It is extremely widely used in research studies worldwide. The conditions of use of a WIP is that it is not to be used for clinical interpretation and that it should be used under IRB approved protocols.

5.2 Efficacy Evaluations

The measures used to assess efficacy of STX209 are:

1. Change from baseline to STX209 administration in left and right superior temporal gyrus auditory M50, M100 and MMF latencies. To measure M50 (40-90ms) and M100 (90-180ms) STG latency (and amplitude), pre-stimulus baseline activity will be subtracted, and right and left M50 and M100 superior temporal gyrus latency and amplitude calculated from the largest amplitude point in the scoring windows using in-house MatLab software. These extended latency ranges allow for M50 and M100 latencies observed in younger children and for low frequency (e.g. 300Hz) stimuli.
2. Change from baseline to STX209 administration in left and right superior temporal gyrus auditory gamma total power and phase-locking measures (examined pre- and post-stimulus). Calculation of single-trial phase/magnitude for right and left STG sources will use complex demodulation procedures[18] implemented in BESA 5.3™, using frequencies between 4 and 80Hz, in steps of 2Hz. Continuous data will be analyzed relative to the tone onset every 25ms, using +/-39.4ms and +/- 2.83Hz (FWHM parameters) of contiguous data at each step. For evoked activity, background activity at each frequency (average power -400 to -100ms) will be subtracted. In addition to evoked power, for each time-frequency bin, a measure of phase-locking referred to as inter-trial coherence (ITC) will be computed, according to $ITC = \text{abs} \left\{ \frac{1}{N} \sum_{k=1}^N e^{i\phi(k)} \right\}$, where N is the number of trials, and $\phi(k)$ is the phase of the signal in the k^{th} trial. ITC is a normalized measure with ITC=1 reflecting no phase variability and ITC=0 reflecting maximal phase variability across trials. The above time-frequency measures will be obtained for the pure-tone and steady-state tasks.

5.2.1 Diagnostic Tests, Scales, Measures, etc.

The following methods will be used to determine whether initial diagnostic criteria and inclusion/exclusion criteria are met, as well as to assess efficacy of intervention. They are listed with their timing of administration. The list provides an overview/summary of all measures given to child participants and their primary caregivers, including screening measures.

Screening - Contact Prior to Visits to CHOP	Approximate Time Demand
Parent/Legal Guardian	
Study description phone script	10 min
Collected by Phone:	
Verbal Consent for Phone Screening	5 min
Screen for Eligibility Criteria	10 min
Pre-Intake Questionnaire (Demographics)	20 min
Subtotal:	75 min
Screening Visit:	
Medical, Diagnostic, and Neuropsychological Assessments	
Procedures administered to Parent/Legal Guardian (at the same time as child testing)	
Intervention History Form	15 min
Medical History Form	30 min
Child Behavior Checklist (CBCL) (if applicable)	20 min
Social Communication Questionnaire (SCQ) (if applicable)	5 min
Social Responsive Scale-II (SRS-II) (if applicable)	10 min
Vineland Adaptive Behavior Scale (if applicable)	20 min
Autism Diagnostic Observational Scale (ADOS-2) (if applicable)	60 min
Subtotal:	2 hours and 40 min
Procedures individually administered to children:	
Physical Examination	15 min
Blood Draw	10 min
Vital Signs	10 min
Clinical Evaluation of Language Fundamentals (CELF –IV)	
(if applicable)	60 min
Wechsler Abbreviated Scale of Intelligence (WASI-II) (if applicable)	60 min
Baseline SMURF	20 min
MRI Mock Scan (optional)	30 min
Subtotal:	3 hours and 25 min

* Diagnostic and neuropsychological testing will not occur if testing scores are available (less than 12 months prior to screening visit) for re-recruited participants (data from tests will only be used if subjects who previously participated in one of our research studies, agreed to share their data on future studies). Only the medical assessments (e.g., vital signs, physical exam, medical history, intervention history form, and blood draw) will be completed for re-recruited participants at screening visit. Therefore, the screening visit will last approximately 80 minutes for re-recruited participants.

MEG Assessment 1: Visit 1

Procedures individually administered to participants at Visit 1	
Autism Diagnostic Interview – Revised (ADI-R) (if applicable)	180min
Vital Signs	10 min

Pre Drug MEG Scan	45 min
MRI Scan	30 min
Administration of STX209/Placebo	< 10 min
MRI Scan continued	30 min
Break	30-60 min
Post Drug MEG Scan	45 min
Adverse Event Assessment (SMURF)	20 min
Subtotal:	4 hours and 50 min

MEG Assessment 2: Visit2

Procedures individually administered to participants at Visit 2	
Vital Signs	10 min
Pre Drug MEG Scan	45 min
MRI Scan	30 min
Administration of STX209/Placebo	< 10 min
MRI Scan continued	30 min
Break	30-60 min
Post Drug MEG Scan	45 min
Adverse Event Assessment (SMURF)	20 min
Subtotal:	4 hours and 10 min

MEG Assessment 3 + Close Out: Visit3

Procedures individually administered to participants at Visit 3	
Vital Signs	10 min
Pre Drug MEG Scan	45 min
MRI Scan	30 min
Administration of STX209/Placebo	< 10 min
MRI Scan continued	30 min
Break	30-60 min
Post Drug MEG Scan	45 min
Physical Examination	15 min
Adverse Event Assessment (SMURF)	20 min
Subtotal:	4 hours and 40 min

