Although this study did not show statistically significant effects of STX209 on irritability symptoms, subjects showed evidence of global behavioral improvement. Subjects' most troublesome behaviors as judged by the parents/caregivers/legally authorized representatives (LARs) were rated on a Visual Analog Scale (VAS) as more improved when the subjects were on STX209 compared to placebo ($p < 0.05$). In the Per Protocol (PP) study population, more clinicians and parent/caregivers rated the subjects' behavior as preferable on STX209 versus placebo by a 2:1 ratio. A post-hoc analysis showed that subjects with higher baseline scores on the Lethargy/Social Withdrawal scale of the ABC-C showed significantly greater improvement on that scale when treated with STX209, as well as on the Vineland Adaptive Behavior Scales-II (VABS-II) Socialization domain ($p < 0.050$ for both comparisons). These subjects also showed significantly greater improvement on multiple measures of global improvement, including the CGI-I, CGI-S, and blinded treatment preference ratings by the clinicians and by parent/caregivers ($p \leq 0.010$ for all comparisons) (22001 Clinical Study Report). No significant safety or tolerability concerns were apparent in Study 22001. Overall, 58 (92.1%) of 63 subjects reported AEs; the percentage was the same (45 subjects, 71.4%) during treatment with STX209 and placebo. AEs with incidence $> 5\%$ and greater than twice the incidence in placebo included headache, sedation (both 8% on STX209 versus 2% on placebo), fatigue, and vomiting (both 6% on STX209 versus 2% on placebo).

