5.4 Primary Endpoint

The primary endpoints are (1) change from baseline to STX209 administration in left and right superior temporal gyrus auditory M50, M100 and MMF latencies, and (2) change from baseline to STX209 administration in left and right superior temporal gyrus auditory gamma total power and phase-locking measures (examined pre- and post-stimulus).

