5.6 Statistical Methods

Primary statistical analyses assess baseline versus post acute-dose (placebo, STX209 15 and 30 mg) changes for (1) M100 auditory latency, and (2) post-stimulus auditory gamma-band activity. For each dependent measure, ANOVAs with dose as a repeated measure will examine baseline versus post acute-dose changes (analyses showing no significant differences across time in baseline M100 and gamma measures will allow use of a single averaged baseline measure). Contrasts of *a priori* interest assess (1) a baseline versus post-acute dose change in the dependent measures averaging across STX209 15 and 30 mg, as well as (2) a change in dependent measures from baseline versus STX209 15 mg versus STX209 30 mg, with this test demonstrating an effect of dose. Secondary and exploratory analyses examine baseline to post acute-dose response changes in MRS auditory GABA concentration as well as associations between MEG functional measures and MRS GABA concentration.

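### Inter-trial coherence, a primary measure, depends on the number of accepted trials, and the plan neither equalizes trial counts nor corrects for them

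*Combined protocol and SAP*

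**What the plan says.** Section 5.2 (Efficacy Evaluations) gives the formula ITC = |(1/N) Σ exp(iφ_k)|, "where N is the number of trials", and adds that "ITC is a normalized measure with ITC=1 reflecting no phase variability and ITC=0 reflecting maximal phase variability across trials". It applies the measure to two tasks: "The above time-frequency measures will be obtained for the pure-tone and steady-state tasks".

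Section 5.4 makes "auditory gamma total power and phase-locking measures (examined pre- and post-stimulus" a primary endpoint, and 5.6.2 repeats this as a principal hypothesis. Section 5.6 is narrower: it limits the primary analysis to M100 latency and post-stimulus gamma-band activity. The first a priori contrast in 5.6 and 5.6.2 is "a baseline versus post-acute dose change in the dependent measures averaging across STX209 15 and 30 mg".

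On trial numbers, 5.1.6 describes the steady-state task as "presenting 200 trials of 40 Hz amplitude modulated (AM) sinusoidal tones", the same in every recording. The pure-tone task is "Binaurally presented 300 and 500Hz 300ms duration sinusoidal tone (45dB SL" and lasts 2 minutes, with no trial count. Section 5.1.6 allows eye-movement and cardiac electrodes. The documents contain no artefact-rejection rule, minimum accepted-trial count, matching of counts or correction for N.

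Section 1.3 reads greater post-stimulus gamma ITC after treatment, in one adolescent, as normalization.

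**The concern.** The absolute mean of N unit vectors cannot be negative. Random phases therefore do not average to 0; they leave a positive residue that shrinks as N grows. Two recordings with identical neural phase-locking but different accepted-trial counts have different expected ITC.

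The first a priori contrast sets baseline against the two active doses and leaves placebo out, so even a difference in trial count that is common to all post-dose recordings would enter it as a change. If fewer trials were kept post-dose, the bias would point toward what Section 1.3 calls normalization. If more were kept, it would hide a true increase.

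Pre-stimulus ITC is the most exposed. The steady-state inter-stimulus interval is jittered, so true phase-locking before the stimulus should be close to zero, where the dependence on N is strongest.

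**Working it through.** **The plan's own figure.** The plan states no figure for ITC bias or retained trials. The nearest is the power of about 0.70 for gamma activity in Section 5.7. It cannot be reproduced, because neither the effect size nor its SD is given. With 36 subjects and two-sided 0.05 it would need a standardized paired effect of about 0.43. It does not bear on what follows.

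**Inputs**
- Estimator: Section 5.2, no correction for N.
- Steady-state trials presented: 200 per recording (5.1.6).
- Pure-tone trials: not stated; 50 assumed.
- Accepted trials: not stated; the drops below are assumptions.
- True ITC, written ρ: not stated; 0 to 0.50 shown.

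**Step 1. Random phase.** E[ITC] ≈ sqrt(π/(4N)).
- N = 200: sqrt(3.1416/800) = 0.063
- N = 150: sqrt(3.1416/600) = 0.072
- N = 100: sqrt(3.1416/400) = 0.089

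From 200 to 100 trials the ratio is sqrt(2) = 1.41, a 41% rise with no neural change.

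**Step 2. Some true phase-locking.** Mean ITC was simulated with von Mises phases. The rise in expected ITC with ρ unchanged is:

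| Accepted trials | ρ = 0 | ρ = 0.10 | ρ = 0.20 | ρ = 0.50 |
|---|---|---|---|---|
| 200 to 180 | 0.003–0.004 | 0.002 | 0.001 | <0.001 |
| 200 to 150 | 0.010 | 0.005 | 0.002 | 0.001 |
| 200 to 100 | 0.026 | 0.014 | 0.006–0.007 | 0.002 |
| 50 to 35 (pure tone, assumed) | 0.024 | 0.02 | 0.012 | 0.004 |

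**Step 3. Effect on a paired test.** Setting: 36 subjects, no true change, nominal two-sided 0.05, and an assumed within-subject SD of change of 0.03. Monte Carlo error is about 1 to 2.5 percentage points.
- 200 to 140 trials: rejection rate 0.21 at ρ = 0, 0.06 at 0.10, about 0.05 at 0.20.
- 200 to 100: 0.66, 0.18 and 0.08.
- 200 to 180: at most 0.08.
- 50 to 35: 0.26, 0.16 and 0.08.

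A larger SD would lower these rates. Averaging over time-frequency bins would raise them, because it reduces noise but not bias.

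**Step 4. Does a correction work?** For independent trials, E[ITC²] = ρ² + (1 − ρ²)/N. Hence E[(N·ITC² − 1)/(N − 1)] = (Nρ² + 1 − ρ² − 1)/(N − 1) = ρ², free of N. Check at ρ = 0.10:
- N = 200: E[ITC²] = 0.01 + 0.99/200 = 0.01495, and (2.99 − 1)/199 = 0.010.
- N = 100: E[ITC²] = 0.01 + 0.99/100 = 0.0199, and (1.99 − 1)/99 = 0.010.

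With equal counts before and after dosing, simulated rejection rates were 0.03 to 0.07 in every setting, which is nominal within Monte Carlo error.

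**The case against.** A reader might infer that trials will be lost after dosing and that ITC will therefore rise and imitate a drug effect. The documents do not support that. They are silent on retained trials, present the same 200 steady-state trials in each recording, and provide short acquisition blocks with breaks. The adverse-event rates that might be cited, "headache, sedation (both 8% on STX209 versus 2% on placebo", come from a titrated, repeated-dose crossover in fragile X syndrome with 4-week treatment periods. They are not trial-loss rates after a single dose. Sedation could also reduce movement, so that more trials are kept and ITC is biased downward. Neither unequal counts nor the direction is established.

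The 41% rise is likewise a worst case, needing no phase-locking and loss of half the trials. A 40 Hz steady-state task is designed to evoke phase-locking, so zero is a poor reference for its post-stimulus window.

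Placebo is also part of the design. The primary objective requires comparison with placebo and the repeated-measures ANOVA includes that condition. Trial loss common to all visits would cancel there, leaving only loss that differs by dose. The first a priori contrast does not have that protection.

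Finally, Section 5.6 confines the primary analysis to post-stimulus gamma activity, which would take pre-stimulus ITC out of it. Sections 5.4 and 5.6.2 list pre-stimulus measures as primary all the same, so the text conflicts.

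These points limit the size and certainty of the problem. They do not alter the behaviour of the estimator or supply the missing safeguard.

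**Conclusion.** The point holds in conditional form. A primary measure is described as normalized but depends on the number of accepted trials, and the plan does nothing to equalize or adjust for that number. Any imbalance in accepted trials between recordings would bias the baseline comparison, in a direction set by which recording keeps more.

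The size rests on assumed counts. With 200 trials presented, the bias is negligible at about 10% loss. It stays small when true ITC is 0.20 or more, unless about half the trials are lost. It matters with heavier loss and true ITC near 0.10 or below, which includes the pre-stimulus window, and in the pure-tone task if its trial count is as low as assumed. The rejection rates also depend on the assumed SD of 0.03. This should be corrected because the remedy is cheap; the documents do not show that a false result is likely.

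**What to change.** In Section 5.2, choose one of the following before the data are analysed:

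1. Analyse the bias-corrected squared phase-locking value (N·ITC² − 1)/(N − 1) in place of ITC. State that it is on the squared scale and can be slightly negative.
2. For each subject and task, subsample the recordings being compared to a common accepted-trial count and average ITC over repeated random draws. Set a minimum count so that one poor recording does not degrade the others.

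Under either option, state the artefact-rejection rule, give the pure-tone trial count, and report accepted trials by dose and time point. If baselines are averaged over visits, average the per-recording values; pooling trials would itself make N unequal. Replace the sentence saying that 0 reflects maximal phase variability, and make 5.4, 5.6 and 5.6.2 agree on whether pre-stimulus ITC is primary.

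The cost is a few lines of code and some wording, with no new data. Option 1 changes the scale of the endpoint; option 2 makes ITC slightly noisier in recordings that had more trials.
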